#### 8.5.2.4 Biochemistry

The following will be analysed according to Section  $\underline{2}$ :

- ALAT
- Albumin
- Alkaline phosphatase
- Amylase
- ASAT
- Bilirubins, total
- Calcium (albumin corrected)
- Chloride
- Creatinine kinase
- Creatinine
- Gamma glutamyltransferase
- CRP
- Estimated GFR, only at Visit 1, 63 and 89
- Lactate dehydrogenase
- Lipase
- Magnesium
- Phosphate
- Potassium
- Sodium
- Total proteins
- Urea (blood urea nitrogen)
- Uric acid

eGFR will be calculated by the central laboratory based on the creatinine value using the CKD-EPI equation as this indirect measurement of GFR has a median difference with direct measurement of GFR of 2.5 ml/min  $\frac{37}{2}$ .

CONFIDENTIAL

Date: Version: Status: Page: 07 May 2015 2.0 Final 74 of 141

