# 12.6.2 Liraglutide

When initiating treatment with liraglutide, the subject may in some cases experience loss of fluids/dehydration, e.g. in case of vomiting, nausea or diarrhoea, sometimes with a decrease in kidney function. It is important to avoid dehydration by drinking enough fluids.

From clinical trials and marketed use overdoses have been reported up to 40 times the recommended maintenance dose (72 mg). Events reported included severe nausea and severe vomiting. None of the reports included severe hypoglycaemia. All patients recovered without complications.

For further information, please refer to the current version of the NN9211 IB.

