Carbohydrate intake		х	х	x	х	x	x	×	x	×	x	×	х	х	х	х	х	х	х	х	x	×	x	х		×
SAFETY																										
Adverse events	х	х	х	×	х	x	x	×	x	×	х	×	x	х	х	х	х	×	×	x	x	×	x	x		х
Hyperglycaemic episodes		x	x	x	x	x	x	×	×	×	×	×	×	x	×	x	x	×	x	×	x	×	x	x		×
Hypoglycaemic episodes		х	х	x	Х	х	X	X 3	x	×	х	×	х	х	х	х	х	×	x	x	х	×	x	х		×
Technical complaints			х	×	х	х	x	x X	x	×	х	×	x	х	х	х	х	x	х	x	x	×	x	х	_	х
Body measurements 	Х	х	Х		Х	Х		2	X		Х		Х		Х		х		Х		Х	~	X	Х		
ECG	x 		х		х						х				х							^	2			
Eye examination			$\mathbf{x}^7$					_																		
Physical examination	Х		х		х						х				х							~	2			
Vital signs	х		х		х	х		~	x		х		х		х				х			~	y			
Antibodies:								_																		
Anti-NNC0114-0006 antibodies			х					_							х							~	y			
Anti-liraglutide antibodies			х												х							^	3			
IgE			х		х				_		х				х							^	3		_	
Biochemistry	х		х		х						х				х							~	X			

Protocol Amendment 5 Trial ID: NN9828-4150	UTN: Eudra	UIII	11-11: 10.: 20	54-71 14-00	72 1215-	39		V 6	ate: ersion			0	02 Ma	ly 201	0 F	tatus: age:					F 11 o	inal f 17	Nov	o Noi	rdisk		
Trial periods	S		R												Treatı	nent											
Visit type: C: Clinic, P: Phone contact	С	С	С	Р	о С	0	- H	0	Р	Р	С	Ρ	С	Ρ	С	Р	С	Р	С	P (	I D	0	- I	0	P	С	
Visit number	I	7	£	1	9	0	0	01	11	15	٤I	14,15	91	81'71	61	50-55	53	54	52	87-97	67	05	10	58	98	28	
Timing of visit (weeks (W), or days (D) if specified)	-D14 -D28 to	-D10	0	ID	IM	+ 7M		T/M	+ †M	SW UT	9M	8°LM	6M	11'01M	71M	\$1-EIM	91M	LIM	81M	17-61 M	77.M	57.M	±7 M	8C/M	00/11	0EM	
Visit window (days)		# 4					- +	+ -	+	+	+ σ	- +	+ σ	- +	+ σ	+	+ σ	+	+ π	+ -	+ ~	н сл н –	 – т		+ -	-H .C	
Coagulation parameters	Х		х		x						х				х							~	X				
Haematology	Х		х		x		_				х				Х							~	×				
Cytokines			х								х				х							~	ć				
Urine dipsticks	Х		х		x						х				х							~	×				
Hepatitis B	Х							х					Х				х				×			x			
Hepatitis C	х																										
Tuberculosis screening test (QuantiFERON)	х																										
Epstein-Barr virus	х							х					х				Х			~	×			х			
CMV 	х						_	x					х				Х	_		~	×			x			
HIV	х																										
Hormones	х														х							~	ć				
Lipids			х												х							~	ζ				
OTHER ASSESSMENTS																											
PK sampling NNC0114-0006			 х		x	~		x			х		Х		х				х			~	ζ			Х	
PK sampling Liraglutide 			х		x	y		x			х		х		Х				х			2	X			х	
TRIAL MATERIAL																											

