## 2 Statistical considerations

Based on the statistical model, treatment means or geometric means (LSMeans) and treatment comparisons (i.e. treatment differences or treatment ratios) will be presented with 95% confidence intervals (CI) and p-values for the two-sided test of no treatment difference. A significance level of

5% will be used. All pairwise treatment differences (or ratios) will be presented. No adjustment for multiple testing will be performed.

Some endpoints will be summarised for the treatment period, for the observation period and for the entire trial period (i.e. the treatment period together with the observation period)

The treatment period and the observation period will be derived for completed subjects as

- The start of the treatment period will be the date of first trial product administration
- The end of the treatment period will be the date of the visit at week 54 (i.e. the day of visit 63)
- The start of the observation period will be the day after the end of the treatment period
- The end of the observation period will be the date of the last visit

For withdrawn subjects the date of last contact will be the maximum of the date of the last visit and the withdrawal date. The treatment period and the observation period will be derived for withdrawn subjects as

- The start of the treatment period will be defined as described for completed subjects
- The end of the treatment period will be as defined for completed subjects if this date is before or on the date of last contact. Otherwise the end of the treatment period will be the date of last contact
- An observation period will only be defined if the date of last contact is after the end of the treatment period
  - The start of the observation period will be defined as for completed subjects
  - The end of the observation period will be the date of last contact

For endpoints evaluated as change from baseline and/or for baseline adjustment in the statistical analyses, baseline will be defined as the information recorded at the Visit 3 (randomisation). If no measurement is available at Visit 3, then the information recorded at Visit 2 will be used as the baseline. Furthermore, if no measurement is available at Visit 2, then the information recorded at Visit 1 will be used as the baseline.

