### **Diabetes complications, eye examination and physical examination**

The eGFR endpoint will be log-transformed and analysed using normal linear regression model with treatment, stratum and sex as fixed factors and age and baseline value as covariates. Treatment means (LSMeans) and treatment ratio for the back-transformed results will be presented with 95% CIs. The analysis will not account for missing data.

All endpoints will be summarised. The endpoints for eGFR will be presented graphically.

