  - The endpoints will be analysed using normal linear regression model for the endpoint with treatment, stratum and sex as fixed factors and age and baseline value as covariates. Treatment means (LSMeans) and treatment differences will be presented with 95% CIs. The analysis will not account for missing data. The number of insulin injections will be derived as the average of the reported number on the three days prior to visit 3, 63 and 89.
- As only the insulin doses prior to visit 3, 63 and 89 will be transferred from the eDiary, the calculation of the endpoint “The number of weeks the subject is off bolus insulin” is not derived based on the dose information in the eDiary as originally planned, but based on the question in the CRF “Has the subject stopped taking bolus insulin since last visit”.
- The following analysis has been deleted in alignment with standard in GLP-1 trials:
  - A normal linear mixed effect model will be fitted to the 7-point SMPG profile data at week 54. The model will include treatment, time-point, the interaction between treatment and time-point, sex and stratum as fixed factors, age as a covariate and subject as a random effect. The variance-covariance matrix will be unstructured and may depend on treatment if an assumption of equal variance-covariance matrix between treatments turn out not to be reasonable. From this model the treatment

differences at each time-point will be estimated and explored. The same analysis will be made using the 7-point SMPG profile data at week 80

- For the analysis of within-subject variability of the before breakfast SMPG, it has been deleted that the 95% CI will be calculated using the delta method. Furthermore it has been clarified that the analysis will not account for missing data.
- As eGFR is only assessed at visit 1, 63 and 89, the statistical analysis has been changed from a MMRM to a normal regression model. Furthermore, it has been specified that the analysis will be done for the log-transformed endpoint:
  - The eGFR endpoint will be log-transformed and analysed using normal linear regression model with treatment, stratum and sex as fixed factors and age and baseline value as covariates. Treatment means (LSMeans) and treatment ratio for the back-transformed results will be presented with 95% CIs. The analysis will not account for missing data.
- Added:

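### eGFR is derived at only three visits although creatinine is drawn at twelve, so the between-arm eGFR analysis gives up early values and protection against dropout that existing samples could supply

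*SAP*

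**What the plan says.** Protocol section 8.5.2.4 (Biochemistry) lists creatinine as a panel item without a visit limit, and lists "Estimated GFR, only at Visit 1, 63 and 89". The same section states that "eGFR will be calculated by the central laboratory based on the creatinine value using the CKD-EPI equation". Protocol section 17.4.1.2 plans to analyse eGFR with a model similar to that for the primary endpoint, i.e. repeated measures.

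SAP section 3 changes this: "As eGFR is only assessed at visit 1, 63 and 89, the statistical analysis has been changed from a MMRM" to a normal regression model. SAP section 2.4.1.2 (Diabetes complications, eye examination and physical examination) specifies log eGFR regressed on treatment, stratum, sex, age and baseline, and adds: "The analysis will not account for missing data".

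Baseline under SAP section 2 is Visit 3, failing that Visit 2, and then: "Furthermore, if no measurement is available at Visit 2, then the information recorded at Visit 1 will be used as the baseline".

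eGFR is a supportive safety endpoint, grouped with retinopathy as a diabetes complication, from baseline to weeks 54 and 80 (SAP section 1.1.2.2).

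**The concern.** The restriction governs which creatinine values are converted to eGFR, not which are collected. The SAP treats it as if the data did not exist. Compare insulin dose: there the SAP also drops the repeated-measures model, but because only three time points are transferred from the e-diary, so the intermediate data really are unavailable. Compare amylase and lipase too: they belong to the same panel, share its schedule, and keep the repeated-measures model (SAP section 2.4.1.2, Laboratory safety variables).

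Two things are at stake. First, protocol section 12.6.2 says that subjects starting liraglutide may in some cases lose fluid, "sometimes with a decrease in kidney function", and section 18.1 says gastrointestinal events are most frequent early in treatment; yet the first post-baseline eGFR comparison is at week 54. Second, subjects who leave before week 54 contribute nothing from their earlier visits, although creatinine from those visits is in the database.

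**Working it through.** **Visits.** From the biochemistry rows of the flow charts (protocol section 2; the original and the versions reprinted in Amendments 2, 3 and 5 agree):

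- Visit 1 (screening, day -28 to -14), Visit 3 (week 0), and Visits 6, 13, 19, 31, 43, 55 and 63 (weeks 1, 6, 12, 24, 36, 48 and 54)
- Visits 74 and 89 (weeks 65 and 80), and Visit 90 (safety follow-up, early withdrawals only)

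| | As planned | eGFR from every creatinine |
|---|---|---|
| Visits with eGFR | 3 | 12 (11 for a completer) |
| Baseline | Visit 1 | Visit 3 |
| Post-baseline values to week 54 | 1 | 7 |
| Post-baseline visits eligible for the SAP's repeated-measures models | 2 (weeks 54, 80) | 8 (weeks 6, 12, 24, 36, 48, 54, 65, 80) |

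Eligibility follows the visit list in SAP section 2, which omits week 1.

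**Attrition.** Protocol section 6.1 plans 304 randomised and expects 240 to reach the primary endpoint: 304 - 240 = 64, and 64/304 = 21.1%. With equal allocation, 76 per arm fall to 60.

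**Precision if dropout is unrelated to eGFR.** The planned regression is then unbiased. Relative to complete data its standard error is sqrt(76/60) = 1.125, about 12.5% larger. To see how much of that the earlier values recover, let r be the correlation between the last earlier on-treatment eGFR and week 54, with all 76 having the earlier value. The variance of an arm mean is proportional to

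(1 - r²)/60 + r²/76, against 1/60 for observed cases only.

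The documents give no r, so it is assumed. For r = 0.5: 0.75/60 + 0.25/76 = 0.01579; multiplied by 60 this is 0.947; its square root is 0.973, a reduction of 2.7%.

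| Assumed r | Reduction in standard error |
|---|---|
| 0.3 | 1% |
| 0.5 | 3% |
| 0.7 | 5% |
| 0.9 | 9% |

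**Bias if dropout is related to eGFR.** A regression on observed cases remains valid if dropout depends only on terms in the model (treatment, stratum, sex, age, baseline). It can be biased if dropout depends on eGFR observed after baseline. A repeated-measures model that includes those values allows for such dependence, provided dropout depends only on what was observed. The documents give no eGFR standard deviation, expected difference or dropout mechanism. A simulation would return whatever dependence was put into it, so no size is claimed.

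**What the model change alone costs.** The protocol's model stood beside the same three-visit limit, so it would have had only weeks 54 and 80. A subject who withdraws before week 54 would normally lack both. Restoring the model without deriving the intermediate values would therefore recover almost nothing at week 54; the two changes belong together.

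**The case against.** The best defence is that the schedule fits the endpoint. eGFR is defined as a long-term complication measure at weeks 54 and 80, and diabetes complications are recorded at Visits 1, 63 and 89. That stands: a reader might infer a contradiction between the documents, and there is none.

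A reader might also infer that early renal decline goes unobserved. It does not. Creatinine, urea and electrolytes are measured from week 1; abnormal values are flagged and listed and all are summarised and plotted (SAP section 2.4.1.2); investigators review the laboratory reports, and clinically significant worsening is an adverse event (protocol section 8.5). What is missing is a between-arm eGFR analysis before week 54.

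Nor does every withdrawn subject lack a late value. Protocol section 8.1.7 asks investigators to aim for Visit 63-type procedures at withdrawal, so 64 is a ceiling. The SAP does not say whether such a value counts as week 54, which is a narrower gap.

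The Visit 1 baseline follows the stated rule and precedes randomisation in every arm. It is further from the start of treatment than it need be, but it does not bias the comparison.

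Finally, nothing in the documents shows that eGFR drives dropout. No withdrawal criterion in protocol section 6.6 is renal, subjects are aged 18 to 45 with eGFR below 60 ml/min excluded, and protocol section 3.1 reports no apparent independent effect of liraglutide on eGFR. The trial cited there was in type 2 diabetes with moderate renal impairment, so it does not settle the matter for newly diagnosed type 1 diabetes, but it argues against presuming harm.

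**Conclusion.** The point holds as a low-cost improvement to one supportive safety endpoint. The plan leaves unused six on-treatment creatinine values before week 54, and a Visit 3 baseline, all already collected. The limited schedule does not compel the analysis chosen, as the treatment of amylase and lipase shows.

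Its size is modest where it can be stated: up to 64 of 304 subjects (21%) without a week-54 value, and a standard-error gain of about 3% at an assumed correlation of 0.5. The stronger case is protection against dropout that depends on earlier eGFR, together with a modelled comparison during the period in which the protocol itself expects fluid loss. It would be tempting to conclude that the planned analysis understates renal harm from liraglutide. The documents do not support that: they supply neither evidence of eGFR-related dropout nor figures from which to size a bias.

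**What to change.** 1. In protocol section 8.5.2.4, or as a derivation in the SAP, have eGFR calculated from every scheduled creatinine by the CKD-EPI method the central laboratory already applies at Visit 1.
2. Use Visit 3 as the eGFR baseline under the general rule, with Visit 1 if Visit 3 is missing.
3. Replace the regression with the repeated-measures model used for amylase and lipase, on log eGFR, at weeks 6, 12, 24, 36, 48, 54, 65 and 80. All of these are in the SAP's visit list.
4. Summarise week 1 descriptively.
5. State how an eGFR from a withdrawal visit is assigned.

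The change should be recorded before the interim database lock, when the sponsor becomes unblinded. The cost is some derivation and programming and a wording change in the protocol or SAP. No extra blood or visits are needed.
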